11.3.3. Alloimmune Quiescence and Operational Tolerance (kSPOT)

[name] Lab has identified an initial tolerance footprint of 49 genes by microarray and qPCR in peripheral blood samples from 75 renal allograft recipients and 16 healthy individuals from the U.S. and in Europe (Brouard S, 2007). 21/49 genes correctly segregated tolerance and chronic rejection phenotypes with 99% and 86% specificity, and the signature was shared with 8% and 50% respectively of stable patients on triple immunosuppression and low-dose steroid monotherapy respectively. The gene signature suggested a pattern of reduced co-stimulatory signaling, immune quiescence, apoptosis, and memory T cell responses, and additionally suggested that TGF β might contribute to this process. This panel has been reduced to a minimal 3-gene signature (BNC2, CYP1B1, KLF6) called SPOT (Spontaneous Tolerance Test) using penalized logistic regression modeling. The inclusion of SPOT in the proposed trials will therefore provide an assessment of immune quiescence that may then be deployed as a measure for the success of Treg therapy. Additionally, these results provide a proof of concept for successfully linking the gene expression profiles in peripheral blood with the peripheral blood phenotype measured by flow cytometry.

Sample collection and analysis plan for kSPOT. Please refer to kSORT for all sample collection and processing. The 21 gene logistic regression score for a tolerance like signature (Roedder S, 2014) will determine immune quiescence profile for all samples in the TASK study and will evaluate if this signature is more likely to be found in patients who have received Treg therapy.

11.3.4. Non-HLA Antibody Assays for Prediction of Chronic Allograft Injury (nHLA-Ab)

The [name] Lab has identified and validated a de novo panel of 6 nHLA- Ab (MIG, ITAC, IFN- γ , GABPA, IL8, CCL21, GDNF) at 6 months post-transplant as important and previously unrecognized triggers of subsequent chronic graft injury (Sigdel TK, 2012). This panel positively correlated ($r=0.78$; $p<0.01$) with the chronic allograft damage index (Yilmaz S, 2003) scores at 2 years with 80% sensitivity and 100% specificity. This discovery involved the use of high-throughput screening of serum IgG interactions in post-transplant recipient sera to 9000 unique full-length human proteins using the Protoarray (Invitrogen) protein array technology and data analysis by customized algorithms (Li L, 2009). The [name] Lab has generated customized reverse ELISA assays for this panel of nHLA-Ab to be easily multiplexed on the Meso Scale Discovery® (MSD) platform. These specific nHLA-Ab panels will be correlated with histological chronicity and change in eGFR in the different treatment arms of the study.

Sample processing analysis plan for nHLA MSD ELISA will be carried out following the protocol developed in the [name] lab. Briefly 15 ng antigen will be coated on to the wells using 50 μ L coating at 0.3 μ g/ml. The plates will be stored at 4 °C overnight. The following day the coating solution is removed and the plate is blocked by 150 μ l Blocker A (at RT, 450 rmp) for 1 hr. After 1 hr the plate will be washed 3 times with 300 μ l wash buffer. Next, 25 μ l of diluted samples will be added and incubated at RT with 450 rpm for 2 hr. This will be followed by washing step followed by addition of 25 μ l detection antibody SULFO-TAG Goat anti Human (Meso Scale Discovery, Gaithersburg MD, Cat# R32AJ-5) (1:1000 dilution) for 1 hr. After this step the plates will be washed and 150ul/well of 1X read buffer (MSD Gaithersburg MD, Cat#

R92TC-2) will be added to each well. The plates will be read immediately using MESO QuickPlex SQ 120 scanner. Relative signal intensity will be used to measure relative abundance of the nHLA antibodies in the samples. The data will be analyzed by Mann-Whitney test using GraphPad Prism software. Spearman correlation will be done to correlate nHLA Ab signal with histological chronicity and change in eGFR in the different treatment arms of the study. These specific nHLA-Ab panels will be correlated with histological chronicity and change in eGFR in the different treatment arms of the study.

11.3.5. Markers of Tubular Epithelial Injury and Renal Fibrosis

Urine and serum markers of renal injury have been associated with subsequent graft fibrosis and failure. Preliminary studies in [name] laboratory have identified urinary TGF β , connective tissue growth factor (CTGF) and the integrin ligand vitronectin as associated with allograft injury and fibrosis (Cheng O, 2008) (Mannon RB, 2010). In addition, urinary ANXA11, α 3 and β 3 integrins and TNF- α have been found to be closely associated with acute alloimmune mediated injury in kidney transplant recipients (Srivastava M, 2011) but have not yet been analyzed prospectively. A novel link under study is between innate immune activation and allograft fibrosis, and measures of HMGB1 and HSP 27 in serum and urine will be of value (Harris HE, 2012) (Lotze M, 2005). The recent association of resistin with brain death and delayed graft function (Oltean S, 2013), as well as the association of acute inflammation, endothelial activation and fibrosis (Jackson AM, 2014) suggest this as a protein that can be measured in this prospective cohort. Having such targets is critical while investigating therapies which may mitigate inflammatory injury that leads to subsequent graft failure in order to monitor the success or failure of treatment. Other relevant targets for monitoring include expression of matrix molecules such as collagens I and III (Mannon R, 1999) and fibroblast infiltration such as α -SMA as indicators of developing fibrosis (Cheng O, 2008) as well as recently described markers of myeloid fibroblast infiltration including MCP-1, CXCL16 and adiponectin (Yang J, 2013). Establishing a link between these markers and graft histology/ renal function is a unique feature of this proposal in which protocol biopsies provide a "hard endpoint" in the subjects' management.

11.4. Stored Plasma and Serum

Plasma and serum will be collected on the day of planned infusion, prior to polyTreg administration for subjects in Group 2. If a need arises during the course of the study, testing may be performed on archived specimens (e.g. CMV, BK, DSA etc.).

12. Biospecimen Storage

Biological specimens (i.e., whole blood, plasma, serum, urine supernatant, urine pellet) obtained under this protocol may be used in future assays to reevaluate biological responses as additional research tests are developed over time. Residual specimens collected at time points planned for the core mechanistic studies will be maintained to allow specimens to be stored for possible use in new assays that have yet to be optimized or conceived, or assays performed by other CTOT members for cross-validation studies. Appropriate informed consent will be obtained for both the collection and storing of samples. During the funding period, samples will be identifiable, which means samples will be coded with a subject ID number that could be directly linked to the subject and the subject's medical record. The specimens from these evaluations may be stored beyond the funding period. Samples will be identifiable, which means samples will be coded with a subject ID number that could be directly linked to the subject and the subject's medical record. When the funding period is over, data from the clinical database will be de-identified, meaning patient identifiers will be removed, and all associated date information will be transformed to study days. Core laboratories and/or repositories maintaining specimens will not have the ability to identify a subject or access data associated with a specimen without specific approval from the study team.

13. Criteria for Participant Completion and Premature Study Termination

13.1. Participant Stopping Rules and Withdrawal Criteria

Participants may be prematurely terminated from the study for the following reasons:

1. The participant elects to withdraw consent from all future study activities, including follow-up.
2. The participant is “lost to follow-up” 3 months after the date of a missed study visit (i.e., no further follow-up is possible because attempts to reestablish contact with the participant have failed).
3. The participant dies.
4. The Investigator no longer believes participation is in the best interest of the participant.
5. CTCAE Grade 3 or higher infusion reaction.
6. Failure to manufacture and supply the cellular product two times for the same subject.

13.2. Participant Replacement

Participants who are prematurely terminated from this study following infusion of at least 100×10^6 Tregs will not be replaced. Subjects who are prematurely terminated prior to polyTreg infusion will be replaced.

13.2.1. Follow-up after Early Study Withdrawal

If a participant in Group 2 is withdrawn from the study for any reason, the participant will be asked to complete a final visit for safety assessment at 52 weeks after polyTregs (Day 364/Visit 6 on Appendix 3).

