3.2. Primary Safety Endpoints

The safety of polyTregs (Group 2) will be described in comparison with CNI-based maintenance IS therapy (Group 1) by:

1. The timing and incidence of Banff 2A or higher acute cell-mediated rejection and/or acute antibody mediated rejection
2. The timing and incidence of study defined Grade 3 or higher infection

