14.4. Collection and Recording of Adverse Events**14.4.1. Collection Period**

Adverse events will be collected from the time of first study mandated procedure until a subject completes study participation or until 30 days after he/she prematurely withdraws (without withdrawing consent) or is withdrawn from the study.

Note that the study eligibility is performed as a standard of care surveillance biopsy with no collection of research specimens. The eligibility biopsy is not considered a study mandated procedure for these reasons.

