14.4.3. Recording Adverse Events

Throughout the study, the investigator will record adverse events and serious adverse events as described previously (Section 14.2, *Definitions*) on the appropriate AE/SAE eCRF regardless of the relationship to study therapy regimen or study procedure.

Once recorded, an AE/SAE will be followed until it resolves with or without sequelae, or until the end of study participation, or until 30 days after the subject prematurely withdraws (without withdrawing consent)/or is withdrawn from the study, whichever occurs first.

14.5. Reporting of Serious Adverse Events and Adverse Events**14.5.1. Reporting of Serious Adverse Events to Sponsor**

This section describes the responsibilities of the site investigator to report serious adverse events to the sponsor via the AE/SAE eCRF. Timely reporting of adverse events is required by 21 CFR and ICH E6 guidelines.

Site investigators will report all serious adverse events (see Section 14.2.3, *Serious Adverse Event*), regardless of relationship or expectedness within 24 hours of discovering the event.

For serious adverse events, all requested information on the AE/SAE eCRF will be provided. However, unavailable details of the event will not delay submission of the known information. As additional details become available, the AE/SAE eCRF will be updated and submitted.

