Primary Endpoint(s)	
Primary Safety Endpoint
 
Participants will be followed for safety for the full duration of study. The safety of polyTregs (Group 2) will be described in comparison with CNI-based maintenance IS therapy (Group 1) by:
 

1. The timing and incidence of Banff 2A or higher acute cell-mediated rejection and/or acute antibody mediated rejection,

2. The timing and incidence of study defined Grade 3 or higher infection

 
Primary Efficacy Endpoint
 
The change in inflammation as measured by the percentage area of cortex occupied by inflammatory cells using computer-assisted quantitative image analysis on the biopsy 7 months after group allocation, expressed as the percent change relative to the baseline biopsy.
 
Primary Mechanistic Endpoint
 
The immunologic profiles of kidney transplant recipients using graft common response module (CRM) gene expression of rejection and/or evidence of

NIH/NIAID/DAIT  
 {Statistical Analysis Plan - Protocol #}CTOT-21

	inflammation in biopsies at 2 weeks after infusion (Group 2) and 7 months after group allocation (Groups 1 and 2).

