#### 4. ANALYSIS SAMPLES

**Modified Intent-to-Treat Sample 1 (mITT1)** – The mITT1 sample consists of all subjects allocated to the CNI-based treatment regimen or received polyTregs while on study.

**Modified intent-to-Treat Sample 2 (mITT2)** – The mITT2 sample consists of all subjects who received polyTregs (Group 2).

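### The 52-week safety visit after early withdrawal is requested of Group 2 only, and it is unclear whether its findings count, so late severe infections could be ascertained unequally

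*Protocol*

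**What the plan says.** Protocol 13.2.1 is the only rule on visits after early withdrawal: "If a participant in Group 2 is withdrawn from the study for any reason, the participant will be asked to complete a final visit". The visit is a safety assessment 52 weeks after infusion, identified as Day 364/Visit 6 of the Group 2 schedule. Nothing comparable is written for Group 1, although Protocol 10.6 and Appendix 2 give Group 1 a Visit 6 at Day 405.

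Protocol 14.4.1 collects adverse events "until a subject completes study participation or until 30 days after he/she prematurely withdraws (without withdrawing consent) or is withdrawn from the study". Protocol 14.4.3 limits follow-up of a recorded event in the same way: "or until 30 days after the subject prematurely withdraws (without withdrawing consent)/or is withdrawn from the study, whichever occurs first". Neither section distinguishes the groups.

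On the analysis side:

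- Protocol 3.2 frames the primary safety endpoints as a contrast: "The safety of polyTregs (Group 2) will be described in comparison with CNI-based maintenance IS therapy (Group 1) by" the timing and incidence of severe or antibody-mediated rejection and of Grade 3 or higher infection.
- SAP section 3 adds: "Participants will be followed for safety for the full duration of study".
- The SAP 4 analysis set, mITT1, "consists of all subjects allocated to the CNI-based treatment regimen or received polyTregs while on study".
- SAP 8.1.2 compares incidence by Fisher's exact or Cochran-Mantel-Haenszel tests, and time of event by ANOVA, Kruskal-Wallis or t-test.
- SAP 9.1 does not impute missing safety data. SAP 7.1.2 generally includes all data whenever they were assessed.

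**The concern.** Taken together, these rules can let a late event be found in one group and missed in the other. A withdrawn Group 2 participant may be seen again at 52 weeks. A withdrawn Group 1 participant has no scheduled contact once 30 days have passed.

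The planned tests use crude proportions and raw event times, with no censoring and no adjustment for observation time. For severe infection, which is analysed in all of mITT1, a Group 1 participant who leaves early would in effect count as event-free for the unobserved remainder. A late infection found at the Group 2 visit would add to that group's incidence and enter its timing summary. The distortion would make polyTregs look worse. It would not hide harm, but it could suggest harm that is not there.

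The texts also leave a gap of their own. Section 13.2.1 schedules a safety assessment that can fall well after the collection period of 14.4.1 has closed, and neither document says whether its findings are to be recorded and analysed.

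**Working it through.** **The plan's own figures.** There is none for the safety comparison: Protocol 15.5 does no sample size calculation for it. The computed design figure is efficacy power. For a 30-point difference, SD 15 and 7 per group, a two-sided t-test at 0.05 has 12 degrees of freedom and noncentrality (30/15) × √(7/2) = 3.74. Power is 92.9%, matching Table 11. This point does not affect it.

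**Are the final visits parallel?** Group 1's T0 visit is Day 41, and 41 + 364 = 405. The Group 1 visit that would match Group 2's Day 364 is therefore already on the schedule.

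**Two readings of the texts.**

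- If the 30-day limit of 14.4.1 and 14.4.3 governs everyone, collection closes equally. The rule then adds no difference between groups.
- If 13.2.1 extends ascertainment for Group 2, a Group 1 participant withdrawn on day *w* loses 405 − (*w* + 30) days that a Group 2 participant could keep: 327 days for *w* = 48, 250 for *w* = 125 and 152 for *w* = 223.

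**Illustration under the second reading.** The documents give no withdrawal or event rate, so the following are assumptions: the same true 405-day risk *p* in both groups, constant hazard, *k* of 7 Group 1 participants withdrawn on day *w*, and complete capture of Group 2 withdrawals at their final visit.

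- Hazard: λ = −ln(1 − *p*)/405
- Risk observed in a withdrawn Group 1 participant: *o* = 1 − exp[−λ(*w* + 30)]
- Expected Group 1 incidence: [(7 − *k*)*p* + *k o*]/7
- Understatement: *k*(*p* − *o*)/7

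Example with *p* = 20%, *w* = 125, *k* = 1: λ = 0.2231/405 = 0.000551 per day and *o* = 1 − exp(−0.000551 × 155) = 0.082. Group 1 incidence is (6 × 0.20 + 0.082)/7 = 18.3% against 20.0%, a gap of 1.7 points.

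Understatement of Group 1 incidence, in percentage points:

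| Assumed risk | Withdrawals | Day 48 | Day 125 | Day 223 |
|---|---|---|---|---|
| 10% | 1 of 7 | 1.1 | 0.9 | 0.5 |
| 10% | 3 of 7 | 3.4 | 2.6 | 1.6 |
| 20% | 1 of 7 | 2.3 | 1.7 | 1.0 |
| 20% | 3 of 7 | 6.8 | 5.1 | 3.0 |
| 30% | 1 of 7 | 3.3 | 2.5 | 1.4 |
| 30% | 3 of 7 | 10.0 | 7.4 | 4.3 |

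With the same final contact in both groups, or with no withdrawals, the gap is 0 under these assumptions.

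**Scale.** One event in a group of 7 is 1/7 = 14.3 points. Fisher's exact test gives p = 0.070 for 4/7 against 0/7 and first falls below 0.05 at 5/7 against 0/7 (p = 0.021). One extra late event would change the described proportions but would not on its own produce a significant difference from a zero count.

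**The case against.** A reader might infer that safety follow-up after withdrawal is required only in Group 2, and that the primary safety comparison is therefore unequal. The documents do not support that. The visit is requested, not required. The 30-day collection covers every subject and may close ascertainment equally. SAP 7.1.2 admits data whenever assessed, but that presupposes the data were collected. A reader might also think that no analysis rule could restore balance; a common cut-off in both groups would.

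Few participants are exposed. Those who die, are lost, or withdraw consent to all follow-up (Protocol 13.1) are unlikely to attend in either group. Manufacturing failure precedes infusion, and recipients not infused are reassigned to Group 1 (Protocol 3.7, SAP 6.2). What chiefly remains is investigator decision and Grade 3 or higher infusion reaction. The latter can occur only after infusion, which is a plausible product-safety reason for a Group 2 visit.

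The effect on rejection is small. Protocol 8.3 places no protocol biopsy at Visit 6, the study definitions tie severe cellular rejection to a Banff grade with clinical treatment, and the SAP restricts the rejection analysis to participants with Banff data. The visit could bring an outside for-cause biopsy to light but would add little else. Protocol 1.2 says graft loss and death will be compared, but they are not primary safety endpoints under section 3.2. The comparison is descriptive and unpowered (Protocol 15.3.2.2 and 15.5).

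All of this stands and limits the size of the point. It does not settle whether findings at the Group 2 visit count, and a product-specific reason for seeing Group 2 does not justify comparing crude incidences gathered over different periods.

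**Conclusion.** The point holds conditionally. The request for a 52-week safety visit after withdrawal covers Group 2 only, the relation of that visit to the 30-day collection period is undefined, and the planned crude comparison has no protection against unequal observation. Actual imbalance through the Group 2 visit needs early withdrawals, attendance by withdrawn Group 2 participants, and late events that are recorded and analysed. It would bear mainly on severe infection and run against polyTregs.

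The range of about 0.5 to 10 points rests wholly on the assumed risks, withdrawal times and numbers, and on full capture in Group 2; the upper end needs 3 of 7 Group 1 participants to withdraw early at a 30% risk. In a descriptive comparison with 7 per group, this is minor to moderate.

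**What to change.** Reconcile Protocol 13.2.1 with 14.4.1 and 14.4.3 by stating whether events found at a post-withdrawal visit are collected and analysed. Extend the request for a final safety assessment to any withdrawn participant who has not refused follow-up. Use Day 364/Visit 6 for infused Group 2 participants and the existing Day 405/Visit 6 for Group 1. Include recipients reassigned to Group 1 without infusion, for whom a date counted from polyTregs has no anchor.

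If follow-up is already complete, add to the SAP one common post-withdrawal cut-off for both groups, used only in the between-group comparison. List later events separately so that no late safety information on the cell product is lost, and report observation time by group beside the incidences. This is the weaker option.

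The cost is one already-scheduled visit for the few Group 1 withdrawals or, for the fallback, a short SAP addition and one extra summary.

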13.3. Study Stopping Rules

The study may be prematurely terminated for the following reasons:

1. Any CTCAE grade 4 or higher infusion reaction
2. Any study defined grade 4 or higher infection
3. Any diagnosis of malignancy and post-transplant lymphoproliferative disease (except non-melanoma skin cancer)
4. Any graft loss
5. Acute Rejection (Banff grade 2A or higher) or acute antibody mediated rejection within 6 weeks after Treg infusion in 3 of first 5 subjects
6. Any death
7. Inability to manufacture and supply polyTregs in 3 of 5 consecutive subjects assigned to Group 2
8. If there is a total of 8 failed lots of polyTregs at any time during the study.

Any of these events will stop trial enrollment and Treg infusions and require DSMB review (See Section 14.8). Subjects who have already received Treg infusion are eligible for mTOR therapy will remain on current therapy during the data review.

14. Safety Monitoring and Reporting

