15. Statistical Considerations and Analytical Plan	70
15.1. Overview	70
15.2. Measures to Minimize Bias	70
15.3. Analysis Plan.....	70
15.3.1. Analysis Samples	70
15.3.2. Endpoint Assessments	70
15.3.3. Descriptive Analyses	73
15.4. Interim Analyses.....	74
15.5. Sample Size Considerations	74
16. Identification and Access to Source Data	76
16.1. Source Data	76
16.2. Access to Source Data	76
17. Protocol Deviations	77
17.1. Protocol Deviation Definitions	77
17.2. Reporting and Managing Protocol Deviations	77
18. Ethical Considerations and Compliance with Good Clinical Practice.....	78

18.1.	Statement of Compliance	78
18.2.	Informed Consent Process	78
18.3.	Privacy and Confidentiality	78
19.	Publication Policy	79
20.	References	80
	Appendix 1. Donor Assessments	86
	Appendix 2. Group 1 Recipient Schedule of Events	87
	Appendix 3. Group 2 Recipient Schedule of Events	88
	Appendix 4. Manufacturing Timeline	89

Glossary of Abbreviations

CFR	Code of Federal Regulations
COVID-19	Coronavirus Disease 2019
CRF	Case Report Form
CRM	Common Response Module
CTCAE	Common Terminology Criteria for Adverse Events
DAIT	Division of Allergy, Immunology, and Transplantation
darTregs	Donor Alloantigen Reactive T Regulatory Cells
DSMB	Data Safety Monitoring Board
FDA	Food and Drug Administration
GCP	Good Clinical Practice
ICH	International Conference on Harmonization
IND	Investigational New Drug
IRB	Institutional Review Board
kSORT	Kidney Solid Organ Response Test
mTOR	Mammalian Target of Rapamycin
NIAID	National Institute of Allergy and Infectious Diseases
PI	Principal Investigator
polyTregs	Polyclonal T Regulatory Cells
Mycophenolate REMS	Mycophenolate Risk Evaluation and Mitigation Strategy
SAE	Serious Adverse Event
SAP	Statistical Analysis Plan
SAR	Suspected Adverse Reaction
SARS-CoV2	Severe Acute Respiratory Syndrome Coronavirus 2
SCI	Subclinical Inflammation
SOP	Standard Operating Procedure
SUSAR	Serious Unexpected Suspected Adverse Reaction

Study Definitions Page

Acute Cell-mediated Rejection	Banff 2007 Type 1A or higher and clinical treatment for acute rejection. Central reading will be utilized when accounting for study stopping rule and for safety endpoint.
Severe Acute Cell-mediated Rejection	Banff 2007 Type 2A or higher and clinical treatment for acute rejection. Central reading will be utilized when accounting for study stopping rule and for safety endpoint.

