1.3. Secondary Safety Objective for mTOR Therapy

Participants receiving polyTregs will be evaluated for the safety of converting from CNI-based maintenance therapy to mTOR inhibitors after Treg therapy.

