5.5.2. Waiting Period between Infusions

Due to manufacturing constraints, there will be a naturally imposed waiting period of at least 1 week in between infusions. This will provide a window to delay or cancel the next infusion in case a stopping rule has been met. Other than the 1-week manufacturing delay, there will be no mandated waiting period between infusions in the polyTregs treatment arm (Group 2), since the proposed starting dose has been infused safely previously in kidney transplant recipients.

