6.1.3. Everolimus Study Dosing and Administration

The use of everolimus in this trial will deviate from package instructions. Subjects in this trial are enrolled between 3 and 7 months after transplantation and induction therapy is site-specific (not study mandated). Furthermore, subjects will be on tacrolimus at study entry, rather than cyclosporine. In eligible patients, everolimus will be initiated within 2 weeks after kidney biopsy showing resolution of inflammation following Treg infusion. Everolimus will be initiated at a dose of 1.5 mg orally twice daily and titrated, as needed. Subjects will begin everolimus with target trough levels of 3-8

$\mu\text{g/L}$ for 4 weeks while still taking tacrolimus. Everolimus target trough levels will be 6-10 $\mu\text{g/L}$ when tacrolimus is discontinued.

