7.1. Immunosuppressive Medications

7.1.1. Tacrolimus

Target tacrolimus trough levels for this study prior to conversion to everolimus are 4-11 µg/dl, which falls within standard of care. For eligible subjects in Group 2, the tacrolimus dose will be reduced by 50% when everolimus is initiated. Tacrolimus will be discontinued 4 weeks after initiation of everolimus therapy.

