7.4. Treatment of Rejection

Patients who are clinically suspected to have a rejection will undergo a kidney biopsy. Biopsies will be read locally according to the Banff criteria and if acute rejection is diagnosed, it will be treated according to the current standard of care. Samples of blood, urine and kidney tissue will be obtained for mechanistic analysis prior to the treatment. Digital images of the biopsies will also be reviewed later by the central pathology core.

8. Study Mandated Procedures

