10.4. Follow Up Visits

Group 2 participants will have study visits on day 1, 7, 14, 28, 84, 182, and 364 after Treg infusion. Participants in Group 1 will have the same visits in parallel with Group 2 patients, starting 48 days after study group assignment. Please refer to Appendix 2 for Group 1 schedule of events and Appendix 3 for Group 2 schedule of events.

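### The only stopping rule that names rejection closes at about the day tacrolimus is withdrawn, and it covers 5 of the 7 planned polyTreg subjects

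*Protocol*

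**What the plan says.** Protocol section 13.3, rule 5, reads: "Acute Rejection (Banff grade 2A or higher) or acute antibody mediated rejection within 6 weeks after Treg infusion in 3 of first 5 subjects". The stopping-rule row of the SAP's protocol summary (SAP section 3) carries the same window and denominator. Under 13.3 a met rule stops enrollment and infusions and sends the data to the DSMB. Subjects already infused stay on their current therapy meanwhile.

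On conversion, section 1.3 says that polyTreg recipients will be "evaluated for the safety of converting from CNI-based maintenance therapy to mTOR inhibitors after Treg therapy", and section 3.3.2 makes acute rejection the measure. The decision biopsy is at Day 14 after infusion (sections 8.3 and 10.6). After it, "everolimus will be initiated within 2 weeks after kidney biopsy showing resolution of inflammation following Treg infusion" (section 6.1.3). Section 6 halves the tacrolimus dose at that point, and section 7.1.1 says "Tacrolimus will be discontinued 4 weeks after initiation of everolimus therapy". Section 9.3.1 differs: it ties the withdrawal to everolimus having reached its target level and gives no fixed interval.

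On which biopsy reading counts, the Study Definitions page says "Central reading will be utilized when accounting for study stopping rule and for safety endpoint". Section 7.4 says of biopsies done for suspected rejection: "Digital images of the biopsies will also be reviewed later by the central pathology core". No deadline is given.

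**The concern.** Rule 5 and the conversion schedule appear to have been written without reference to each other. The protocol sets out to learn whether taking a subject off the calcineurin inhibitor (CNI) after Tregs is safe with respect to rejection. Yet its only rejection trigger ends at about the time that exposure begins, and it counts only the first five subjects.

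At stake is whether a run of severe rejections after tacrolimus withdrawal would bring the data to the DSMB by rule before the next subject is enrolled or infused, or only because someone chose to ask.

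**Working it through.** The documents give no operating characteristics for rule 5, so there is no stated figure to reproduce. The check is a timeline plus a count.

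**Inputs**
- Rule window: 6 weeks × 7 = Day 42 after infusion (13.3).
- Decision biopsy: Day 14, with ±3 days as read from Table 2 in 10.6, so Day 11 to 17.
- Everolimus start: 0 to 14 days after the biopsy (6.1.3).
- Tacrolimus stop: 28 days after the everolimus start (6 and 7.1.1).
- Last visit: Day 364 (10.4).
- Planned polyTreg subjects: 7 (synopsis).

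**Timeline**

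Tacrolimus stop = biopsy day + delay to everolimus + 28.

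| Case | Biopsy | Everolimus start | Tacrolimus stop | CNI-free days by Day 42 | Half-dose days by Day 42 | CNI-free days to Day 364 |
|---|---|---|---|---|---|---|
| Nominal, earliest | 14 | 14 | 42 | 0 | 28 | 322 |
| Nominal, latest | 14 | 28 | 56 | 0 | 14 | 308 |
| With window, earliest | 11 | 11 | 39 | 3 | 28 | 325 |
| With window, latest | 17 | 31 | 59 | 0 | 11 | 305 |

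The largest share covered is 3/325 = 0.9% of the CNI-free period.

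**Sensitivity to section 9.3.1.** If withdrawal follows the everolimus level, it could come before 28 days. As an outer limit, suppose tacrolimus stopped on the very day everolimus started, at the earliest Day 11. The rule would then cover 42 − 11 = 31 of 364 − 11 = 353 days, or 8.8%. The wording of 9.3.1 implies less, because the target has to be reached first. The conclusion does not depend on which text governs.

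**Cross-check with the SAP.** SAP section 8.2.1 counts rejection after conversion from Day 69 to Day 405 after allocation. If infusion is aligned with Day 41 (the Group 1 T0 visit), Day 69 is 69 − 41 = Day 28 after infusion, and 28 + 28 = Day 56. If it is aligned with Day 48 (Appendix 4), Day 69 is Day 21, and 21 + 28 = Day 49. Either way tacrolimus stops after rule 5 has closed. The SAP follows this period as an endpoint, but no rejection trigger is attached to it.

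**Denominator.** 7 − 5 = 2 subjects (29%) fall under no rejection rule.

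**Comparison within 13.3.** The rules on infusion reactions, infection, malignancy, graft loss and death have no subject cap and no stated time limit. The manufacturing rules use any five consecutive subjects or a cumulative count. Only the rejection rule is confined to an early window and the first five subjects, and no reason is given.

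**Context only: sensitivity inside the window.** P(at least 3 of 5) = 10p³(1−p)² + 5p⁴(1−p) + p⁵. At assumed true 6-week rates of 15%, 30% and 50% this is 2.7%, 16.3% and 50.0%. The documents give no rate. These figures describe the rule before Day 42, not the gap after it.

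**The case against.** The strongest reply is that rule 5 watches for early harm from the cell product, and that conversion is protected in other ways. Section 4.3 limits who may convert: a minimum dose, centrally confirmed resolution of inflammation, and a donor-specific antibody limit. Section 6.4 acts at once for any subject who rejects on everolimus. Rejection is reported within 24 hours with no time limit (14.2.4). The investigator, protocol chair and medical monitor can suspend enrollment and initiation of treatment at any time (14.8.1). The DSMB meets at least yearly and can be convened ad hoc (14.8.2, 14.8.3). A rule that fired late would not by its terms end everolimus already under way.

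All of that stands, and it rules out four stronger readings that a reader might infer.

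- *Late rejection can never halt the trial.* Not so. One graft loss or one death stops it automatically, in any subject and at any time, and rejection can lead to either. Discretionary suspension is also available.
- *No study-level rule sees any of the conversion.* Not so. Conversion begins when tacrolimus is halved, and 11 to 28 half-dose days fall inside rule 5's window for the first five subjects.
- *The whole withdrawal falls in a gap between visits.* Section 10.4 says "Group 2 participants will have study visits on day 1, 7, 14, 28, 84, 182, and 364 after Treg infusion", so no scheduled visit falls between Day 28 and Day 84, and the final stop (Day 39 to 59) lies there. But the halving nominally occurs by the Day 28 visit. Section 6.2 requires at least weekly trough levels, and section 10.5 provides unscheduled visits if creatinine rises.
- *Open-ended central reading contradicts section 5.5.2.* That section says of the gap between infusions: "This will provide a window to delay or cancel the next infusion in case a stopping rule has been met". This speaks of a rule already met. The missing deadline is an omission that weakens the safeguard, not a contradiction.

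What the reply does not answer is the absence of a predefined rejection trigger for the CNI-free period. Graft loss and death are the outcomes that a rejection trigger is meant to precede. Section 6.4 protects the subject who has already rejected, not the next one to be enrolled or infused.

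**Conclusion.** The concern holds in a limited form. No predefined rejection rule covers essentially any of the CNI-free period (0 to 3 of about 305 to 325 days), and 2 of the 7 planned polyTreg subjects are under no rejection rule at all. Severe rejection after withdrawal that stops short of graft loss or death can halt enrollment and infusions only through discretionary review under 14.8.

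This rests on the fixed 4-week interval of sections 6 and 7.1.1, on the ±3-day window for the Day 14 biopsy, and on reading the first five subjects as the first five infused with polyTregs. The gap matters only for subjects who convert, and the documents do not predict how many will. It is an inexpensive safety improvement. Patient-level management of rejection is not in question.

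**What to change.** Reconcile 13.3 rule 5 and its SAP copy with sections 6.1.3 and 7.1.1 and objective 1.3, so that a predefined trigger for DSMB review of severe rejection reaches the period after everolimus conversion and all infused subjects. The sponsor and DSMB should set the window, denominator and count, and state when a central reading counts toward the rule. No particular threshold is proposed here.

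In the same amendment, reconcile the timing of tacrolimus withdrawal in sections 6 and 7.1.1 (a fixed 4 weeks) with section 9.3.1 (when everolimus reaches target).

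The cost is amendment wording in the protocol and the SAP summary, and possibly one more ad hoc DSMB review or a short pause. No new procedures or subjects are needed.
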